After randomization, pre-intervention activities must begin within 48 hours of completing Baseline assessments, as applicable per appendix.

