9 SAFETY ASSESSMENTS AND REPORTING

9.1 ADVERSE EVENTS AND SERIOUS ADVERSE EVENTS

9.1.1 DEFINITION OF ADVERSE EVENTS AND SERIOUS ADVERSE EVENTS

An AE is any untoward medical occurrence in humans, whether or not considered intervention-related, which occurs during the conduct of a clinical trial. An AE can therefore be any change in clinical status, routine labs, x-rays, physical examinations, etc., that is considered clinically significant by the site investigator.

An SAE or serious suspected adverse reaction or serious adverse reaction, as determined by the investigator or the sponsor, is an AE that results in any of the following serious outcomes:

- Death
- Life-threatening AE ("life-threatening" means that the study participant was, in the opinion of the investigator or sponsor, at immediate risk of death from the reaction as it occurred and required immediate intervention)
- Persistent or significant incapacity or substantial disruption of the ability to conduct normal life functions
- Inpatient hospitalization or prolongation of existing hospitalization
- Congenital abnormality or birth defect
- An important medical event that may not result in one of the above outcomes, but may jeopardize the health of the study participant or require medical or surgical intervention to prevent one of the outcomes listed in the above definition of a serious event

For those interventions that include a device, the following additional definitions will apply.

An Adverse Device Effect (ADE) is an event related to the use of an investigational medical device. This includes any AE resulting from insufficiencies or inadequacies in the instructions for use, deployment, implantation, installation, operation, or any malfunction of the investigational medical device. This also includes any event that is a result of a use error or intentional misuse.

- Device malfunction the failure of a device to perform in accordance with the instructions for use or clinical investigative plan.
- User error or intentional misuse a device is used in a manner that is an act or omission of an act that results in a different medical device response than intended by the manufacturer or expected by the user.

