9.1.2 COLLECTION PERIOD OF AE AND SAE INFORMATION

Safety event collection will occur at the pre-specified study visits but all participants will be instructed to self-report concerns by calling the site.
Serious adverse events (SAEs), UADEs, or ESIs (per appendix) will be extracted by site personnel from the participant's medical record if the participant seeks medical care or if hospitalization occurs, each of which notifies the site to conduct follow-up.

Medical occurrences that begin before the first invasive study procedure (blood collection or nasal swab), but after obtaining informed consent, will not be considered an AE. The medical occurrence or condition will be captured on the Medical History electronic case report form (eCRF).

Non-serious AEs may be reported by the participant, but will not be collected into the study database as an AE or further assessed by the site or study personnel. Non-serious AEs that result in study intervention discontinuation will be identified as the reason for study intervention discontinuation in the study database and reported separately as an AE, and they will be collected from the start of study intervention administration through the end of the intervention.

Any AEs that are also classified as symptoms associated with PASC and collected during the study will not be collected as a safety event to the study database or further assessed by the site or study personnel because they will be collected as part of the PASC symptom dataset.

Serious adverse events (SAEs) will be collected from the first invasive study procedure (blood collection or nasal swab) through the End of Study for all appendices that use a study drug and through the EOI Clinic Visit for all appendices that include other interventions.

UADEs will be collected in the clinical database from the start of the intervention through the end of the intervention.

Adverse events (AEs) that qualify as an ESI, even if a non-serious AE, will be collected from the start of the study intervention through the End of Study (30 ± 3 days after EOI) for all appendices that use a study drug and through the EOI Clinic Visit for all appendices that include non-drug interventions.

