9.1.4 REPORTING AND MONITORING OF SAES FOR STUDY DRUG(S) OR UADES FOR DEVICE(S)

Study drugs used in this platform protocol are not approved for the indication for the treatment of PASC. The DSMB will review aggregate safety data according to the DSMB Charter.

Any UADE(s) that a platform protocol principal investigator determines is/are reportable will be submitted to the manufacturer, all reviewing IRBs, and all participating site investigators within 10 working days of when the platform protocol principal investigator makes that determination.

If the platform protocol principal investigator determines that a UADE presents an unreasonable risk to participants, all investigations or parts of investigations presenting that risk shall be terminated as soon

as possible. Termination shall occur no later than 5 working days after the sponsor makes this determination and no later than 15 working days after the sponsor first received notice of the effect.

Individual SAEs or UADEs must be entered into the data system within 24 hours of site awareness. After receiving that data, within 1 to 2 business days the DCRI Safety Surveillance team will notify pharmaceutical partners of SAEs (if applicable) and device manufacturers of UADEs that occur involving the specific appendix of the supplied study drug/control or supplied device, as required.

Serious adverse events (SAEs) that are related to the study drug and confirmed unlisted by the DCRI Safety Medical Monitor and platform protocol principal investigator will be reported to the central IRB as SUSARs — as 7-day reports for unexpected fatal or life-threatening adverse reactions and 15-day reports for serious and unexpected adverse reactions. The SUSARs will be shared with the pharmaceutical partner of the supplied study drug according to the same timelines, if applicable. If the DSMB notes a clinically important increase in the rate of a SUSAR, the platform protocol principal investigator will notify site investigators no later than 15 calendar days after determining that the information qualifies for reporting. The site investigators will notify their local IRBs according to local guidelines, if applicable. Refer to the Safety Management Plan for details regarding specific reporting timelines.

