14.1.2 SCHEDULE OF ADDITIONAL PROCEDURES

The full schedule of procedures from Table 3 is shown for operational ease starting on the next page. Table 3 abbreviations: EOI – End of Intervention; PASC – Post-acute sequelae of SARS-CoV-2 infection; PROMIS – Patient-Reported Outcomes Measurement Information System

Procedures	Pre- randomization Visits	Baseline Visit	Pre- intervention	Intervention		End of Study
Study weeks	Wk-6 to -1	Day 0	Wk 1	Wk 2-8	EOI Clinic Visit ¹⁶ Wk 9	EOI + 30 days
Informed consent, platform	Х					
PROMIS8a SRI and 8b SD	Х	X ¹⁷			Х	Х
Sleep-screening questions	Х					
Demographics	Х					
Concomitant medications	Х	X ¹⁷			Х	
Medical history	X ¹⁸					
Pregnancytest	Х	X17				
Nasal swab	Х	X ¹⁷				
SRBD screening/HSAT ¹⁹	Х					
Appendix-level eligibility criteria	Х					
Informed consent, appendix level	Х					
RANDOMIZATION		Х				
Height (H) and weight (W)		H/W			W	
Sleep Phenotype questionnaire		Х				
PROMIS10a Fatigue		Х			Х	
ECog2		Х			Х	
Neurocognitive Battery		Х			Х	
PASC Symptom Questionnaire		Х			Х	
ISI		Х			Х	
ОНQ		Х			Х	
DSQ-PEM		Х			Х	

Table 3. Schedule of Procedures for Appendix B - Complex PASC-Related Sleep Disturbance

¹⁶ An Early Termination Clinic Visit will be request for participants who prematurely discontinue the study intervention. This visit will mirror the EOI Clinic Visit and obtain as much data as the participants allow. Refer to Section 8.6.

¹⁷ If necessary; see Baseline visit, Section 8.3

¹⁸ At every clinic visit after screening visit, changes in medical history including SARS-CoV-2 infection since last visit will be collected.

¹⁹ Not necessary if participant has had a sleep apnea screening and documented adherence within 6 months of Screening

Procedures	Pre- randomization Visits	Baseline Visit	Pre- intervention	Intervention		End of Study
Study weeks	Wk -6 to -1	Day 0	Wk 1	Wk 2-8	EOI Clinic Visit ¹⁶ Wk 9	EOI + 30 days
PGIS		Х			Х	
PGIC				Х	Х	Х
Blood for Biorepository		Х			Х	
Stool for Biorepository		Х			Х	
Sleep diary		Distribute	Complete ²⁰		Complete ²⁰	
Activity tracker		Distribute	Wear ²⁰	Wear (optional)	Wear ²⁰	Wear ²⁰
RESET-PASC		Session 1		Sessions 2-5		
SASS-Y + light use		Х		Х		
Blinded melatonin		Distribute		Х	Return	
Blinded tailored light		Distribute	Installation ²¹	X ²²	Х	
Blue Iris light sensor		Distribute	Wear ²⁰	Wear (optional)	Wear ²⁰	
Safety assessment		Х		X ^{23,24}	Х	X ²³
Healthcare Encounter survey				X ²⁴	Х	
Pill count/light adherence				X ²⁵	Х	

²³ Phone call only

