14.4.2 LIGHT DELIVERY METHOD

The modified table/floor lamp will deliver polychromatic white light from up to 12-16 inches from the open eye for at least 1 hour in the morning (within 2 hours of waking, but no later than noon). The table/floor lamp is a controlled plug-in fixture that will be placed on a timer. The timer will be set to turn the light table on at desired wake times and turn it off 4 hours before desired bedtimes.

Participants will also wear a light sensor (Blue Iris Labs Mobile Sensor) to measure existing surrounding lighting during the intervention. The Blue Iris is a personal light meter calibrated to measure circadianeffective light. It can store 60 days of light measurements at 1-min intervals. It will characterize the light exposure of each participant. This light sensor will help verify compliance with the light exposure protocol. Importantly, the Blue Iris is noninvasive, not a medical device, and produces no harmful emissions. Similar to wearing a badge, participants will be asked to wear the device for the duration of the study, but at a minimum for 7 days after TL installation and 7 days before EOI. If they choose not to wear the Blue Iris device for the duration of the study, they will be asked to keep a daily log with the start and end times they were exposed to the intervention.

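### UADE database collection opens at the start of the intervention, but the tailored light is handed out at Day 0 and installed in pre-intervention Wk 1, so UADE collection that week is not assured

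*Protocol*

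**What the plan says.** Section 9.1.2 sets separate collection windows by event type. For device effects, "UADEs will be collected in the clinical database from the start of the intervention through the end of the intervention". For serious events generally, "Serious adverse events (SAEs) will be collected from the first invasive study procedure (blood collection or nasal swab) through the End of Study" in drug appendices and through the EOI visit in others, so SAE collection opens well before Wk 1 in either case.

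Table 3 (section 14.1.2) carries the lamp row as "Blinded tailored light Distribute Installation": distributed under Baseline (Day 0) and installed under Pre-intervention (Wk 1). The Intervention columns are Wk 2-8 and the EOI visit in Wk 9. Section 8.3 adds that "pre-intervention activities must begin within 48 hours of completing Baseline assessments". Section 14.4.2 asks for light-sensor wear "at a minimum for 7 days after TL installation and 7 days before EOI", and Table 3 puts the first of those two periods in Wk 1.

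Section 9.1.1 defines an adverse device effect to include events from "insufficiencies or inadequacies in the instructions for use, deployment, implantation, installation, operation, or any malfunction of the investigational medical device". Its UADE definition has a limb B, which takes in any other unanticipated serious device problem bearing on participants' rights, safety or welfare. Limb B does not require an SAE.

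Section 9.1.4 divides onward notice by type. Pharmaceutical partners are told of SAEs, and "device manufacturers of UADEs that occur involving the specific appendix" describes what goes to the device side. SUSAR reporting is confined to SAEs related to the study drug.

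**The concern.** The window for device effects should open no later than the device reaches the participant. Here the definition of a device effect names deployment and installation, while the window is tied to a later event, the start of the intervention. On the Table 3 timeline, a plug-in lamp is delivered and set up in the home before UADE collection begins.

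The SAE window does not fully substitute for this. The expedited SAE route is for drug-related events, and notice to the device manufacturer is written for UADEs. A limb B problem, such as a serious electrical failure that injures nobody, would not be collected as an SAE. Section 9.1.3 states the duty to document for events inside the pre-specified windows, and Table 3 marks no safety assessment in the Pre-intervention column. At stake is whether a problem in the first days with the lamp is recorded as a device event and brought to those who decide on reporting.

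**Working it through.** No power or error-rate figure is involved. The check sets the windows against the timeline and counts weeks.

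**Timeline for the lamp**

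| Period in Table 3 | Lamp | SAE collection | UADE collection (9.1.2) |
|---|---|---|---|
| Baseline, Day 0 | distributed | open | not open |
| Pre-intervention, Wk 1 | installed | open | depends on what counts as the start of the intervention |
| Intervention, Wk 2-8 | in use | open | open |
| EOI visit, Wk 9 | in use | open | open until the end of the intervention |

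**When does the intervention start?**

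- Table 3: Wk 2-8 is 7 weeks, plus Wk 9 gives 7 + 1 = 8 weeks. This matches the 8 weeks of light in 14.4.3 and the 8 weeks of melatonin in 14.5.4.
- Section 8.4 treats pre-intervention and intervention as separate periods.
- Appendix A counts in the same way: Wk 2-10 is 9 weeks, plus Wk 11 gives 10, the duration stated in 13.1.
- Section 14.1 states 9 weeks for Appendix B. That total is reached only as Wk 1-9, with the pre-intervention week included.

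Most of the text therefore places the start at Wk 2, which leaves Wk 1 outside the UADE window. The 9-week statement points the other way, and nothing in the protocol settles it.

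**Size of the uncovered period**

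- Start at Wk 2: about 7 days. If the full 48-hour allowance between Baseline and Wk 1 is used, 7 + 2 = 9 days from distribution.
- Start at Wk 1: only the allowance between Baseline and Wk 1, up to 48 hours.

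As an upper bound, all four groups receive an active or placebo lamp, so 600 participants x 1 week = 600 participant-weeks, or 1 of the 9 weeks up to EOI (11%). This bound takes the Wk 2 start and a lamp in place for the whole of Wk 1. Table 3 gives no installation day and does not say that the lamp is switched on that week.

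**The case against.** A reader might infer that a lamp-caused serious event in Wk 1 has no device reporting route. The documents do not support that.

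- The sentence in 9.1.2 limits collection in the clinical database. Section 9.1.4 requires submission of any UADE that a platform principal investigator finds reportable, and ties this to no study week. The 10-working-day submission and the 5- and 15-working-day termination limits run from a determination or from notice, and the 24-hour entry rule runs from site awareness.
- A serious Wk 1 event would be collected as an SAE and entered within 24 hours. Its relationship to the study intervention would be assessed under 9.1.2.2, and its expectedness by the safety medical monitor.
- Participants are told to call with concerns, and sites extract SAEs and UADEs from medical records when care is sought.
- If the 9 weeks in 14.1 is taken literally, Wk 1 lies inside the window.
- Section 9.1.4 refers specific reporting timelines to a Safety Management Plan that is not among the documents.

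These points stand, and they remove the claim of a missing route. They do not remove the mismatch. Collection is the step that brings an event to the investigator's determination, an SAE record alone does not trigger notice to the device manufacturer as 9.1.4 is written, and a limb B problem that is not an SAE falls outside both windows if the intervention starts at Wk 2. The appeal to 9 weeks shows that the start date is ambiguous; it does not show that Wk 1 is covered.

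**Conclusion.** The point holds in a limited form. The UADE window in 9.1.2 is not aligned with the lamp's distribution and installation in Table 3, and the start of the intervention in Appendix B can be read in two ways. UADE collection in Wk 1 is therefore not assured, chiefly for a serious device problem that is not an SAE. Serious events as such are not lost, and UADE reporting under 9.1.4 remains available.

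The exposure is about one week per participant if the intervention starts at Wk 2, and up to 48 hours if it starts at Wk 1. The 600 participant-weeks is a ceiling, not an estimate. Section 14.4.1 describes the lamp as non-significant risk, so very few events are expected, although the protocol gives no rate from which to calculate a number. This is a minor correction with no bearing on the efficacy analysis.

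**What to change.** In section 9.1.2, start UADE collection when the device is distributed to the participant (Day 0 in Appendix B) instead of at the start of the intervention. Leave the end of the window as stated; nothing in this point argues for moving it.

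Separately, reconcile the 9-week intervention in section 14.1 with the 8 weeks implied by Table 3 and sections 14.4.3 and 14.5.4, so that windows tied to the start of the intervention have one meaning. Which duration is intended is for the sponsor to state.

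The cost is one sentence in the next amendment plus the reconciliation. No visit is added, and the sample size and analysis are unchanged.

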9.1.2.1 SEVERITY OF EVENT

For reportable events, the following guidelines will be used to describe severity.

- Mild Events require minimal or no treatment and do not interfere with the participant's daily activities
- **Moderate** Events result in a low level of inconvenience or concern with the therapeutic measures. Moderate events may cause some interference with functioning.
- Severe Events interrupt a participant's usual daily activity and may require systemic drug therapy or other treatment. Severe events are usually potentially life-threatening or incapacitating. Of note, the term "severe" does not necessarily equate to "serious" for regulatory reporting.

9.1.2.2 RELATIONSHIP TO STUDY INTERVENTION

All reportable events must have their relationship to the study intervention assessed by the site investigator, who will evaluate the event based on its temporal relationship and his or her clinical

judgment. The degree of certainty about causality will be graded using the categories below. In a clinical trial, the study intervention must always be suspect.

- **Related** The AE is known to occur with the study intervention, there is a reasonable possibility that the study intervention caused the AE, or there is a temporal relationship between the study intervention and the event. Reasonable possibility means that there is evidence to suggest a causal relationship between the study intervention and the AE.
- Not Related There is not a reasonable possibility that the administration of the study intervention caused the event, there is no temporal relationship between the study intervention and event onset, or an alternate etiology has been established.

9.1.3 TIME PERIOD AND FREQUENCY FOR EVENT ASSESSMENT AND FOLLOW-UP

The occurrence of an AE, ESI, UADE, or SAE may come to the attention of study personnel during study visits and interviews of a study participant presenting for medical care, or upon review by a study monitor.

All reportable events will be captured on the appropriate CRF. Information to be collected includes event description, date/time of onset, clinician's assessment of severity, relationship to study intervention (assessed only by those with the training and authority to make a diagnosis), action taken with study intervention (eg, discontinuation), and date/time of resolution/stabilization of the event. All events occurring within the pre-specified reportable time windows must be documented appropriately regardless of the relationship.

Any medical condition that is present at the time the participant is screened will be considered a baseline condition and not reported as a safety event. However, a deterioration of the condition at any time during the study will be recorded as a safety event.

Changes in the severity of a safety event will be documented to allow an assessment of the duration of the event at each level of severity to be performed. Safety events characterized as intermittent require documentation of the onset and duration of each episode.

The site investigator will follow all SAEs or UADEs until resolution, stabilization, or the event is otherwise explained. The DCRI Safety Surveillance Team will follow all SAEs or UADEs until resolution, stabilization, or otherwise explained.

9.1.4 REPORTING AND MONITORING OF SAES FOR STUDY DRUG(S) OR UADES FOR DEVICE(S)

Study drugs used in this platform protocol are not approved for the indication for the treatment of PASC. The DSMB will review aggregate safety data according to the DSMB Charter.

Any UADE(s) that a platform protocol principal investigator determines is/are reportable will be submitted to the manufacturer, all reviewing IRBs, and all participating site investigators within 10 working days of when the platform protocol principal investigator makes that determination.

If the platform protocol principal investigator determines that a UADE presents an unreasonable risk to participants, all investigations or parts of investigations presenting that risk shall be terminated as soon

as possible. Termination shall occur no later than 5 working days after the sponsor makes this determination and no later than 15 working days after the sponsor first received notice of the effect.

Individual SAEs or UADEs must be entered into the data system within 24 hours of site awareness. After receiving that data, within 1 to 2 business days the DCRI Safety Surveillance team will notify pharmaceutical partners of SAEs (if applicable) and device manufacturers of UADEs that occur involving the specific appendix of the supplied study drug/control or supplied device, as required.

Serious adverse events (SAEs) that are related to the study drug and confirmed unlisted by the DCRI Safety Medical Monitor and platform protocol principal investigator will be reported to the central IRB as SUSARs — as 7-day reports for unexpected fatal or life-threatening adverse reactions and 15-day reports for serious and unexpected adverse reactions. The SUSARs will be shared with the pharmaceutical partner of the supplied study drug according to the same timelines, if applicable. If the DSMB notes a clinically important increase in the rate of a SUSAR, the platform protocol principal investigator will notify site investigators no later than 15 calendar days after determining that the information qualifies for reporting. The site investigators will notify their local IRBs according to local guidelines, if applicable. Refer to the Safety Management Plan for details regarding specific reporting timelines.

Site investigators are not obligated to actively seek information on AEs or SAEs after a participant has concluded study participation. However, if site investigators learn of an SAE, including death, at any time after a participant has completed the study (but before the study itself has ended), and they consider the SAE to be reasonably related to the study intervention, the site investigators must promptly report the SAE to the sponsor via Electronic Data Capture (EDC) entry.

